
Statistical Methods
	
The primary efficacy analysis will be performed in accordance with the intention-to-treat principle. All randomized patients will be included in the primary efficacy analysis according to their assigned study treatment, irrespective of the actual treatment received. The primary analysis of safety will include all patients who receive at least 1 dose of study treatment.
 
The primary efficacy endpoint will be PFS. PFS is defined as the time from randomization to the earlier of disease progression or death due to any cause. The primary analysis of PFS will be based on PFS events determined by the IRC according to RECIST 1.1 criteria (Eisenhauer, Therasse et al. 2009). Patients whom enter hospice care, or other such similar end-of-life care, without prior objective evidence of disease progression will be considered to have disease progression for purposes of the primary analysis of PFS. Unless specified otherwise, all recorded PFS events will be included in the primary analysis regardless of stopping randomized therapy. Patients who initiate alternate anticancer therapy in the absence of documented progression will be censored at the latest disease assessment prior to initiation of such therapy. Patients who were last known to be alive and progression-free will be censored at the latest disease assessment. Patients with no baseline or post-baseline disease assessments will be censored at the randomization date unless death occurred prior to the first planned assessment (in which case the death will be considered a PFS event). A secondary analysis of PFS will be performed based on PFS events determined by the local investigator. Sensitivity analyses will be performed to assess the impact of the different censoring mechanisms and deviations from the planned schedule of disease assessments. PFS will be summarized descriptively using the Kaplan-Meier method. The primary inferential comparison between treatment arms will use the log-rank test stratified by the randomization stratification factors. The hazard ratio for treatment will be estimated using a stratified Cox proportional hazards model.
 
For patients with metastatic advanced GPNMB-expressing breast cancer in the treatment setting under investigation, median PFS of 4 months is anticipated following randomization to capecitabine. It is hypothesized that CDX-011 will increase median PFS in such patients by 2.25 months (i.e., 4.0 vs 6.25 months). Under the assumption of proportional hazards, such an increase corresponds to a hypothesized hazard ratio of 0.64.
 
If this hypothesized hazard ratio is true, 203 PFS events (total of two arms) determined by IRC will provide 85% power with 2-sided type I error of 0.05. Under the assumption

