12.5. Statistical Methods

12.5.1. Efficacy Analysis

Progression-free survival

PFS is defined as the number of months from randomization to the earlier of disease progression or death due to any cause. The primary analysis of PFS will be based on PFS events determined by the IRC according to RECIST 1.1 ([Eisenhauer, Therasse et al. 2009](#)). Patients whom enter hospice care, or other such similar care, without prior objective evidence of disease progression will be considered to have disease progression for purposes of the primary analysis of PFS. Unless specified otherwise, all recorded PFS events will be included in the primary analysis regardless of stopping randomized therapy. Patients who initiate alternate anticancer therapy in the absence of documented progression will be censored at the latest disease assessment prior to initiation of such therapy. Patients who were last known to be alive and progression-free will be censored at the latest disease assessment. Patients with no baseline or post-baseline disease assessments will be censored at the randomization date unless death occurred prior to the first planned assessment (in which case the death will be considered a PFS event). A secondary analysis of PFS will be

performed based on PFS events determined by the local investigator. PFS will be summarized descriptively using the Kaplan-Meier method. The primary inferential comparison between treatment arms will use the log-rank test stratified by the randomization stratification factors. The hazard ratio for treatment will be estimated using a stratified Cox proportional hazards model.

Objective response rate

ORR is defined as the proportion of patients who achieve a best overall response of complete or partial response according to RECIST 1.1. The primary analysis of ORR will be based upon evaluations by the IRC. Inferential comparisons between treatment arms will be made using the Cochran-Mantel Haenszel chi-square test, stratified by the randomization stratification factors.

Duration of objective response

DOR is defined as the number of months from the time criteria are first met for either CR or PR, until the first date that PD is objectively documented. Patients without documented disease progression will be handled as described above for the PFS analysis. The duration of objective response will be summarized descriptively using the Kaplan-Meier method. Inferential testing of DOR is not planned.

Overall survival

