10.3 Progression-free Survival (PFS)

PFS is defined as the time from the date of randomization to documented disease progression, or death due to any cause, whichever is earlier.

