10.3.1 Primary PFS Analysis

The primary analysis of PFS will be based on the Independent Review Committee (IRC) assessment according to RECIST 1.1. Unless specified otherwise, all recorded PFS events will be included in the primary analysis regardless of stopping randomized therapy. [Table 3](#) below describes the detailed censoring rules for the primary PFS analysis. The determination of PFS is also detailed in the flow chart in the [Appendix](#) (Section 17).

Table 3: Date of Progression of Censoring for the Primary PFS analysis (IRC)

Situation	Date of Progression or Censoring	Outcome
Disease progression between scheduled disease assessments	Date of progression	Progressed
Death between scheduled disease assessment	Date of death	Progressed
Death before the first planned disease assessment at 6 weeks (plus 1 week window) without any disease assessment	Date of death	Progressed
No baseline disease assessments	Date of randomization	Censored
No post-baseline disease assessments without death before the first planned disease assessment	Date of randomization	Censored
Discontinuation of study treatment without progression (i.e., due to toxicity, withdrew consent, or lost to follow-up) and no further radiographic assessment ^a	Date of last radiological assessment without documented progression disease	Censored
Alternate anticancer treatment started without documentation of disease progression beforehand ^b	Date of last radiological assessment prior to start of further anticancer treatment	Censored
Death or disease progression after missing two or more consecutively scheduled disease assessments ^c	Date of last radiological assessment without documented progression disease prior to death/progression	Censored
Patients who have not progressed and are alive	Date of last radiological assessment without documented progression disease	Censored

a. For a patient who discontinues study treatment without PD and continues to have radiographic assessments, post-treatment radiographic assessments will be considered for PFS analyses according to the rules in this table.

b. Alternate anticancer treatment interventions that are diagnostic (e.g., biopsy) or palliative (e.g., local radiation for painful nodule) will not routinely require censoring unless they are determined to interfere with the assessment of the patients' disease status.

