c. Disease assessments are planned every 6 (± 1) weeks for the first 6 months (24 weeks); and every 9 (± 2) weeks, thereafter, until disease progression. The interval of two missed scheduled assessments is calculated according to the scheduled assessment frequency and the corresponding window (1 or 2 weeks depending on assessments scheduled before or after 6 months).

The median PFS by treatment group will be estimated using Kaplan-Meier method and the Kaplan-Meier curves by treatment group will be presented.

The primary inferential comparison of this endpoint will use the stratified log-rank test stratified by the actual stratification factors corrected in the clinical database after randomization. A secondary analysis based on *the stratification factors as randomized* will also be performed ([Section 4.1](#)). Estimation of the hazard ratio for treatment and its corresponding 95% confidence interval will be determined using a stratified Cox proportional hazards model with the same stratification factors.

Subgroup analyses for PFS ([Section 10.2](#)) will be performed and a forest plot will be presented.

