10.3.3 Sensitivity PFS Analysis

Sensitivity analysis will be performed to assess potential sources of bias due to 1) censoring for alternate anti-cancer therapy; 2) symptomatic disease progression.

Alternate anti-cancer therapy prior to documentation of disease progression

It is anticipated some patients may receive subsequent anti-cancer therapy prior to documentation of progressive disease. Censoring alternative anticancer treatment prior to documented progression may be problematic since it ignores the issue of informative censoring and contravenes the basic principle of an intention-to-treat analysis. Patients who stop taking randomized study treatment prior to documented progression frequently do so due to either toxicity of the drug or due to deterioration in the status of their disease. In such cases, the investigator may judge that immediate intervention, commonly in terms of the introduction of a new cancer treatment, is in the best interest of the patient without necessarily waiting for confirmatory radiographic evidence of progressive disease ([Carroll 2007](#)).

To address the above concerns, the following sensitivity analysis will be performed: Death or disease progression that's documented after the initiation of an alternate anti-cancer therapy will be considered as a PFS event.

Symptomatic progression / hospice care events

A sensitivity analysis will be performed with symptomatic deterioration or admission to hospice care considered a PFS event with investigator's disease assessments. Patients with symptomatic deterioration will be considered to have disease progression the day after the date of the last disease assessment showing no evidence of disease progression. For patients who enter hospice care without prior symptomatic deterioration or disease progression per RECIST 1.1, the date of admission to the hospice care will be considered as PFS event date.

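### The protocol counts hospice entry as progression in the primary PFS analysis; the SAP's PFS definition and Table 3 omit it without declaring the change

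*Protocol*

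**What the plan says.** **Protocol.** The synopsis describes "Patients whom enter hospice care, or other such similar end-of-life care, without prior objective evidence of disease progression" as having progressed, and 12.5.1 repeats that such patients "without prior objective evidence of disease progression will be considered to have disease progression for purposes of the primary analysis of PFS". That analysis is based on IRC-determined events. Neither place gives the event a date. Later in the same paragraph, 12.5.1 adds: "Patients with no baseline or post-baseline disease assessments will be censored at the randomization date unless death occurred prior to the first planned assessment". Table 1, footnote 4, requires hospice admissions to be reported.

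**SAP, primary analysis.** Section 10.3 states: "PFS is defined as the time from the date of randomization to documented disease progression, or death due to any cause, whichever is earlier". Section 10.3.1 bases the analysis on IRC assessment and sets the censoring rules in Table 3. None of its nine rows or three footnotes mentions hospice. One row censors "Death or disease progression after missing two or more consecutively scheduled disease assessments" at the last progression-free scan. The section adds that "The determination of PFS is also detailed in the flow chart" in Section 17; that chart is not shown in the text available.

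**SAP, sensitivity analysis.** Section 10.3.3: "A sensitivity analysis will be performed with symptomatic deterioration or admission to hospice care considered a PFS event". It uses investigator assessments and pools hospice with symptomatic deterioration. The admission date applies only to entrants without earlier symptomatic deterioration; the others are dated the day after their last progression-free assessment.

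**Change control.** Protocol Section 12 lets the SAP modify the plan but requires an amendment for major changes to the primary endpoint definition or its analysis. SAP Section 14 lists only a clarification about measurable disease for ORR. For 12.5.1, the Amendment 4 log hands the SAP the scope of the sensitivity analysis and nothing else.

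**The concern.** A statistician who programs the SAP's visible text produces a different primary analysis from the one the protocol states. No analysis in that text is IRC-based PFS with hospice entry as an event, so the protocol's primary analysis is not run even as a sensitivity analysis. DOR inherits the problem, because both documents carry the PFS handling over to it.

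Hospice entrants are close to progression or death, so censoring them is probably informative. In an open-label trial, the rule should not remain open to choice once results are known.

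**Working it through.** **1. The plan's own figures.** Inputs from Protocol 12.2: medians 4.0 and 6.25 months, HR = 4.0/6.25 = 0.64, 2:1 allocation (p = 1/3), two-sided 0.05, power 85%. Schoenfeld's formula:

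D = (1.960 + 1.036)² / [p(1 − p)(ln 0.64)²] = 8.98 / (0.2222 × 0.1992) = 202.9, so 203 events. This matches.

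Expected events at T = 26 months, with uniform accrual over A = 24 months and λ = ln 2/median, use 1 − [exp(−λ(T − A)) − exp(−λT)]/(λA) per patient. Over 200 and 100 patients this gives 227.3; removing 10% unobservable events leaves 204.5, consistent with 203. The design figures are not in dispute.

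**2. One patient under both texts.** Progression-free scan at week 6, hospice in week 10, no further scans.

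- Protocol: PFS event, undated.
- SAP, alive at cutoff: censored at week 6.
- SAP, dies after missing the week-12 and week-18 scans: censored at week 6. Footnote c says "The interval of two missed scheduled assessments is calculated according to the scheduled assessment frequency and the corresponding window"; adding the one-week window to week 18 gives week 19.
- SAP, dies earlier: event, on the death date.

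Week 10 to week 19 is 9 weeks = 2.07 months. If median survival after entry is 0.75 to 3 months (assumed), the share alive at week 19 is 2^(−2.07/0.75) = 15% to 2^(−2.07/3) = 62%. The SAP censors these patients at week 6.

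**3. A conflict inside the protocol.** Take an entrant with no post-baseline scan who dies after the first planned assessment. The hospice sentence says event; the no-post-baseline sentence says censor at randomization. Neither is ranked. Below, *reading A* lets the hospice sentence prevail and *reading B* the other. Under the planning medians, 21% (capecitabine) and 14% (CDX-011) of PFS times fall before the week-6 scan.

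**4. Simple bound.** If 1%, 2%, 5% or 10% of 203 protocol events were hospice entries that the SAP censors and does not replace, 201.0, 198.9, 192.8 or 182.7 events remain. Schoenfeld power at HR 0.64 is then 84.7%, 84.3%, 83.2% or 81.2%.

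**5. Simulation.** The design is that of step 1, with scans on the protocol schedule and an unstratified log-rank test. Hospice rate, arm imbalance, entry time (drawn from the PFS distribution) and survival after entry (median 0.75 to 3 months) are assumptions. Runs used 20,000 to 40,000 replicates for the month-26 cut, with Monte Carlo error about 0.2 points for power and 0.1 for false wins.

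Power lost by moving from the protocol rule to the SAP rule, month-26 cut, in percentage points:

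| Hospice entry | Reading A | Reading B |
|---|---|---|
| 2% in both arms | 0.2–0.6 | 0.1–0.4 |
| 10% in both arms | 0.6–1.8 | 0.2–1.3 |
| 2% capecitabine, 1% CDX-011 | 0.6–1.4 | 0.3–1.0 |
| 10% capecitabine, 5% CDX-011 | 2.5–6.9 | 1.2–4.9 |

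In the last row, power is 87.5% (A) or 86.2–85.5% (B) under the protocol and 85.0–80.6% under the SAP. The protocol's internal conflict alone is worth 87.5 − 86.2 = 1.3 to 87.5 − 85.5 = 2.0 points.

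If the cutoff waits for 203 events, the equal-10% case loses no power, and the cutoff moves later by 0.5–1.7 months (A) or 0.2–1.3 (B). The 10% versus 5% case still loses 2.2–5.6 points (A) or 1.3–4.1 (B).

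With no true effect and more hospice entry on CDX-011 (5% capecitabine, 10% CDX-011), the one-sided false-win rate at month 26 is 3.4–4.5% under the SAP, against 2.8% (A) or 3.1–3.3% (B) under the protocol. With 1% and 2% it is 2.7–2.9% against about 2.7%.

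**The case against.** The strongest objection is that the flow chart, which the SAP says also details PFS determination, cannot be seen. This stands as a limit on certainty about the SAP as a whole. It does not remove the fault: a hospice branch there would contradict Table 3. The chart's one visible note dates progression by RECIST, which does not suggest such a branch.

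Second, the SAP may modify the protocol, and only major changes need an amendment. Whether this one is major is a judgement. But it alters which patients are primary-endpoint events, the current protocol keeps the hospice sentence, and SAP Section 14 does not record the departure.

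Third, hospice is not ignored: Section 10.3.3 uses it and the data are collected. That makes the protocol's analysis recoverable. It does not restore it, because 10.3.3 uses investigator assessments and adds symptomatic deterioration.

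Fourth, the numbers rest on assumed inputs, and the larger ones need a two-fold imbalance between arms. This is correct. The simulated 87.5% is also 2.5 points above the planned 85%, so the differences between rules should be read, not the absolute levels. At the favourable end of the 10% versus 5% case, the SAP's 85.0% equals planned power.

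Last, footnote c gives no formula. Allowing two intervals of 6 + 1 weeks after week 6 gives week 20, and the 15–62% becomes about 12–59%. The conclusion is unchanged.

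**Conclusion.** The concern holds. The protocol and the visible SAP text give different event rules for the primary endpoint, and the difference is undeclared. Confidence in that textual conflict is high; for the SAP as a whole it depends on the flow chart. The protocol also gives two answers for entrants without a post-baseline scan.

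The numerical effect is unknown. On the assumed ranges it is under 2 power points when entry is equal between arms, and material only if entry is both fairly common and unequal. It should be fixed because an event rule of the sole primary endpoint in an open-label pivotal trial is unsettled, not because of a demonstrated large effect.

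**What to change.** Check the Section 17 flow chart, then, before database lock, reconcile the passages to one primary rule with a stated event date. In both documents, rank it against the no-post-baseline, missed-assessment and alternate-therapy rules.

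- **SAP follows protocol.** Add hospice entry to SAP 10.3 and a Table 3 row: entry into hospice or similar end-of-life care without prior IRC progression; a stated date, for example the admission date already used in 10.3.3; progressed. Align the flow chart. In Protocol 12.5.1 and the synopsis, say which sentence governs an entrant with no post-baseline scan.
- **Protocol follows SAP.** Remove the hospice sentence from the synopsis and 12.5.1 by amendment, and declare the change in SAP Section 14.

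Either way, run the other rule on IRC data as a sensitivity analysis, keep hospice separate from symptomatic deterioration, and report hospice entrants by arm.

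The cost is one table row or a short amendment, a ranking sentence in each document, and one extra analysis run. Hospice admission is already reported, so no new data collection is needed.

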12.5.2. Protocol Therapy and Concomitant Medications

The total number of doses and total dose administered will be tabulated for study treatments. The primary reason for treatment delays, dose reductions and permanent discontinuation of study treatment will be tabulated in a similar manner.

Concomitant medications will be coded using WHO Drug Dictionary. All medication data will be listed individually and summarized by anatomical therapeutic class and preferred name.

12.5.3. Safety Analysis

Safety and tolerability will be assessed by incidence, severity, and changes from baseline of all relevant parameters including adverse events (AEs), ECGs, laboratory values, and vital signs.

AEs will be coded using the latest available version of the Medical Dictionary for Regulatory Activities (MedDRA). The number and percentage of patients experiencing one or more AEs will be summarized by treatment arm, relationship to study drug, and severity. Laboratory parameters will be summarized using descriptive statistics, by post-dosing shifts relative to baseline, and data listings of clinically significant abnormalities. Treatment-emergent AEs are defined as AEs that start on or after the first day study drug is administered. AEs will be summarized by the number and percentage of patients who experienced the event, according to system organ class and preferred term. A patient reporting multiple cases of the same AE will be counted once within each system organ class and similarly counted once within each preferred term. Unless specified otherwise, the denominator for these calculations will be based on the number of patients in each

treatment arm who receive at least one (1) dose of study drug, irrespective of the total number of doses administered. AEs will also be summarized by NCI-CTCAE severity grade and by relationship to study drug. Additional summaries may also be provided for SAEs and events resulting in the permanent discontinuation of therapy. All AEs will be included in individual patient data listings.

Vital sign results (systolic and diastolic blood pressure, pulse, respiration, and temperature) and ECG parameters will be summarized descriptively. Changes will be calculated relative to the assessments at baseline.

The changes in hematology, chemistry, and other laboratory values will be summarized descriptively. The incidence of Grade 3 and 4 hematological toxicities (including neutropenia, thrombocytopenia, and anemia) will be provided. The use of red blood cell and other blood component transfusions and/or growth factor support will be reported. Similar analyses will be done for selected chemistry tests (including liver and renal function tests). Data listings of all laboratory data collected during the study will be presented. Laboratory values outside normal limits will be identified in data listings and will include flags for high and low values.

13. DATA HANDLING AND RECORD KEEPING

13.1. Data Quality Assurance

Monitoring and auditing procedures defined by Celldex or designee will be followed, in order to comply with GCP guidelines. Each center will be visited at regular intervals by a monitor to ensure compliance with the study protocol, GCP and legal aspects. This will include on-site checking of the case report forms (CRF) for completeness and clarity, cross-checking with source documents, and clarification of administrative matters.

To ensure the safety of participants in the study and to ensure accurate, complete, and reliable data, the investigator will keep records of laboratory tests, clinical notes, and patient medical records in the patient files as original source documents for the study. All the information required by the protocol should be provided; any omissions require explanation.

Celldex (or designee) will provide Case Report Forms (CRFs) for the recording and collection of data. The CRF will either be in paper or via an electronic data capture (EDC) system. Entries made in the CRF must be either verifiable against source documents, or have been directly entered into the CRF, in which case the entry in the CRF will be considered as the source data. The source data parameter to be verified and the identification of the source document must be documented. Corrections to CRFs and source data will be made only by authorized members of the study staff, clearly entered, initialed and dated. The investigator will sign the CRFs to indicate that, to his/her knowledge, they are complete and accurate. If further changes are made after this, the investigator will be made aware of the corrections and his/her approval will be documented by re-signing. In cases where an EDC system is utilized, an electronic audit trail is maintained with similar information collected.

The investigator will permit Celldex (or designee) direct access to source data/documents for trial-related monitoring, audits, review, and inspection(s). Through ongoing monitoring visits at the investigational sites, Celldex (or designee) will periodically check the patient data recorded in the CRF's against source documents, to ensure accuracy, completeness, and adherence to the protocol, regulatory compliance, and the maintenance of comprehensive clinical records.

As well, the study may be audited by Celldex (or designee) and/or regulatory agencies at any time. If requested, the investigator will provide Celldex (or designee), applicable regulatory agencies and/or applicable ethical review boards with direct access to original source documents.

